Score:

16. Tremor

- 0 = Absent.
- 1 = Slight and infrequently present.
- 2 = Moderate; bothersome to patient.
- 3 = Severe; interferes with many activities.
- 4 = Marked; interferes with most activities.

Score:

17. Sensory complaints related to parkinsonism

- 0 = None.
- 1 = Occasionally has numbness, tingling, or mild aching.
- 2 = Frequently has numbness, tingling, or aching; not distressing.
- 3 = Frequent painful sensations.
- 4 = Excruciating pain.

Score:

ENTER TOTAL SCORE for PART II. ACTIVITIES OF DAILY LIVING:

(from items 5 to 17 - maximum score = 52)

Total score:

Protocol: 0170														
Visit	Subject ID Number										Rater Initials			
	1	7	0	-						-				

PART III MOTOR EXAMINATION (Acceptable responses are 0, 1, 2, 3, 4)

Please perform full UPDRS approximately 1 to 3 hours after the subject has taken a scheduled dose of their Parkinson's medication, preferably their morning dose). UPDRS in the ON state will be measured at a time representative of the ON state in that subject, not in "best" ON.

18. Speech
 0 = Normal.
 1 = Slight loss of expression, diction and/or volume.
 2 = Monotone, slurred but understandable; moderately impaired.
 3 = Marked impairment, difficult to understand.
 4 = Unintelligible.
 Score:

19. Facial Expression
 0 = Normal.
 1 = Minimal hypomimia, could be normal "Poker Face".
 2 = Slight but definitely abnormal diminution of facial expression.
 3 = Moderate hypomimia; lips parted some of the time.
 4 = Masked or fixed facies with severe or complete loss of facial expression; lips parted 1/4 inch or more.
 Score:

20. Tremor at rest
 Face, lips, chin + Right hand + Left hand + Right foot + Left foot =
 Score:
 0 = Absent.
 1 = Slight and infrequently present.
 2 = Mild in amplitude and persistent. Or moderate in amplitude, but only intermittently present.
 3 = Moderate in amplitude and present most of the time.
 4 = Marked in amplitude and present most of the time.

21. Action or Postural Tremor of hands
 Right hand + Left hand =
 Score:
 0 = Absent.
 1 = Slight; present with action.
 2 = Moderate in amplitude, present with action.
 3 = Moderate in amplitude with posture holding as well as action.
 4 = Marked in amplitude, interferes with feeding.

22. Rigidity (Judged on passive movement of major joints with subject relaxed in sitting position. Cogwheeling to be ignored.)
 Neck + RUE + LUE + RLE + LLE =
 Score:
 0 = Absent.
 1 = Slight or detectable only when activated by mirror or other movements.

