30. Postural Stability (Response to sudden, strong posterior displacement produced by pull on shoulders while subject is erect, with eyes open and feet slightly apart. Subject is prepared.)
 0 = Normal.
 1 = Retropulsion, but recovers unaided.
 2 = Absence of postural response; would fall if not caught by examiner.
 3 = Very unstable, tends to lose balance spontaneously.
 4 = Unable to stand without assistance.

Score:

31. Body Bradykinesia and Hypokinesia (Combining slowness, hesitancy, decreased arm swing, small amplitude and poverty of movement in general)
 0 = None.
 1 = Minimal slowness, giving movement a deliberate character; could be normal for some persons. Possibly reduced amplitude.
 2 = Mild degree of slowness and poverty of movement which is definitely abnormal. Alternatively, some reduced amplitude.
 3 = Moderate slowness, poverty or small amplitude of movement.
 4 = Marked slowness, poverty or small amplitude of movement.

Score:

A. Indicate the subject's PD state during the examination (check one):

- "On" during exam
- Fluctuated during the exam
- "Off" during exam

ENTER TOTAL SCORE for PART III. MOTOR EXAMINATION: Total score:
 (from items 18 to 31 - maximum score = 108)

Protocol: 0170															
Visit	Subject ID Number											Rater Initials			
	1	7	0	-							-				

PART IV. COMPLICATIONS OF THERAPY (In the past week)

A. DYSKINESIAS

32. Duration: What proportion of the waking day are dyskinesias present?
 (Historical information.)

0 = None
 1 = 1-25% of day
 2 = 26-50% of day
 3 = 51-75% of day
 4 = 76-100% of day

Score:

33. Disability: How disabling are the dyskinesias? (Historical information; may be modified by office examination.)

0 = Not disabling.
 1 = Mildly disabling.
 2 = Moderately disabling.
 3 = Severely disabling.
 4 = Completely disabled.

Score:

34. Painful Dyskinesias: How painful are the dyskinesias?

0 = No painful dyskinesias.
 1 = Slight.
 2 = Moderate.
 3 = Severe.
 4 = Marked.

Score:

35. Presence of Early Morning Dystonia (Historical information.)

0 = No
 1 = Yes

Score:

ENTER TOTAL SCORE for PART IV. A. Dyskinesias (from items 32 to 35 - maximum score = 13)

Total score:

SAMPLE NOT TO BE USED

Protocol: 0170															
Visit	Subject ID Number											Rater Initials			
	1	7	0	-											

PART IV. COMPLICATIONS OF THERAPY (In the past week)

B. CLINICAL FLUCTUATIONS

36. Are any "off" periods predictable as to timing after a dose of medication?
 0 = No
 1 = Yes
 Score:

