- A standardized HIPAA/GDPR compliant telemedicine platform will be provided so that site personnel can participate in remote visits that are conducted in the subject's home (or designated location), utilizing Home Health Providers.
- A Home Health Provider (HHP) service has been employed.
- Medically qualified and trained HHP staff employed will visit the subject's home (or designated location) and will work with Site Staff (SS) to conduct each remote study visit from the privacy of the subject's home or designated location (such as a caregiver's home).
- During these remote visits, in coordination with Site Staff, the HHPs will use the Rater Station to facilitate collection of patient reported outcomes, will collect blood samples for safety labs and PK testing, will collect ECGs, and will measure the subject's vital signs.
- All data collected during the remote visits will be transferred to the Investigator and the study site via established processes (either electronically or on paper).

Data signifying where the visit was conducted (in clinic or remote), how the data were collected, and who collected data remotely will be recorded in subject source documents and in the clinical study database.

A Home Health Provider Delegation Log will be used to record the names of HHP professionals who assist Site Staff with the conduct of the remote visits. This separate delegation log will distinguish between those individuals who are part of the site staff (recorded on Site Delegation Log) and those who are employed by the HH Provider.

Logistics Arrangements for Remote Visits:

For remote study visits, the home health personnel conducting the visit will be notified by the clinic-based study staff of each upcoming scheduled visit for the study subject(s). The clinic-based staff will coordinate with the home health personnel to ensure access to all necessary subject source documents, required equipment, and procedural instructions to complete the remote assessment.

Clinic-based staff will participate in the remote study visit(s) via the established telemedicine platform available for the study.

Home health personnel will transfer the source documents completed during the remote visit to the Investigator's site via established processes. Home health personnel will transfer via established secure means the data collected in electronic format to the appropriate data repository for inclusion in the clinical database.

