
100% = Completely independent. Able to do all chores without slowness, difficulty, or impairment. Essentially normal. Unaware of any difficulty.
 
90% = Completely independent. Able to do all chores with some degree of slowness, difficulty, and impairment. Might take twice as long. Beginning to be aware of difficulty.
 
80% = Completely independent in most chores. Takes twice as long. Conscious of difficulty and slowness.
 
70% = Not completely independent. More difficulty with some chores. Three to four times as long in some. Must spend a large part of the day with chores.
 
60% = Some dependency. Can do most chores, but exceedingly slowly and with much effort. Errors; some impossible.
 
50% = More dependent. Help with half, slower, etc. Difficulty with everything.
 
40% = Very dependent. Can assist with all chores, but do few alone.
 
30% = With effort, now and then does a few chores alone or begins alone. Much help needed.
 
20% = Nothing alone. Can be a slight help with some chores. Severe invalid.
 
10% = Totally dependent, helpless. Complete invalid.
 
0% = Vegetative functions such as swallowing, bladder and bowel functions are not functioning. Bedridden.

A medical professional who specializes in Parkinson’s disease assesses each item of the UPDRS. The items in Parts 1–4 yield a possible maximum of 199 points, representing maximal disability, with a score of zero representing no disability. Scores for Parts 1–4 are calculated as the sum of the item scores, excluding items that could not be rated. The total score for Parts 1–4 is calculated as the sum of the scores for the parts.

All UPDRS parts will be completed on Day 1 for De Novo subjects, while only Parts 2 and 3 of the questionnaire will be completed for subjects rolling over from Study 0169. At later visits, only Parts 2 and 3 will be administered.

8.8.3. [REDACTED]
[REDACTED]
[REDACTED]
[REDACTED]
[REDACTED]
[REDACTED]
[REDACTED]

[REDACTED]
[REDACTED]
[REDACTED]
[REDACTED]
[REDACTED]

[REDACTED]
[REDACTED]

[REDACTED]
[REDACTED]
[REDACTED]
[REDACTED]
[REDACTED]
[REDACTED]
[REDACTED]
[REDACTED]

[REDACTED]
[REDACTED]
[REDACTED]

[REDACTED]

[REDACTED]

[REDACTED]

[REDACTED]

[REDACTED]

[REDACTED]	[REDACTED]	[REDACTED]	[REDACTED]
[REDACTED]	[REDACTED]	[REDACTED]	[REDACTED]
[REDACTED]	[REDACTED]	[REDACTED]	[REDACTED]
[REDACTED]	[REDACTED]	[REDACTED]	[REDACTED]
[REDACTED]	[REDACTED]	[REDACTED]	[REDACTED]

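### SAP 8.8 scores a UPDRS item that could not be rated as zero and defines a Parts 1–4 total that exists only for De Novo subjects on Day 1; both need a stated rule, at minor severity

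*SAP*

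**What the plan says.** The UPDRS scoring text stands in SAP 8.8, after the OHQ scoring; its own heading and opening are redacted. The visible part gives three rules.

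- Part scores: each of Parts 1 to 4 is "calculated as the sum of the item scores, excluding items that could not be rated". No proration and no minimum number of rated items is given.
- Total: "The total score for Parts 1–4 is calculated as the sum of the scores for the parts".
- Range: "The items in Parts 1–4 yield a possible maximum of 199 points, representing maximal disability, with a score of zero representing no disability".

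The same text says that De Novo subjects complete every part on Day 1 and that rollover subjects from Study 0169 complete Parts 2 and 3 only. It adds: "At later visits, only Parts 2 and 3 will be administered". Protocol 6.4.6.4 and footnote j of the Schedule of Study Procedures agree.

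For comparison, SAP 8.8.1 averages the nonmissing items of the OHSA and OHDAS, so an absent OHQ item is not scored as zero.

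Protocol 3.4.4 lists change in UPDRS at Week 6 post randomization as an exploratory endpoint for PD subjects, and Protocol 8.5.1.2 analyses it by ANCOVA. SAP 6.3 sets the baseline for that change at Week 16 (V6). SAP 8.1 makes open-label efficacy summaries descriptive.

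**The concern.** Leaving an item out of a sum gives the same result as scoring it 0, and on this scale 0 is the best value. A change score can then reflect which items were rated rather than motor state.

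Unrated items are foreseeable. On the form in Protocol Appendix 2-10, rigidity is "Judged on passive movement of major joints with subject relaxed in sitting position" and postural stability is the "Response to sudden, strong posterior displacement produced by pull on shoulders while subject is erect". Both need hands on the subject. The SAP says a Parkinson's specialist assesses each item, while at remote visits "Clinic-based staff will participate in the remote study visit(s) via the established telemedicine platform available for the study". The home-provider tasks listed in Protocol Appendix 9 do not include motor rating. One visit modality per subject is required only for V6 to V9, and COVID-related exceptions are allowed there.

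The second issue is the total. It is defined over four parts, two of which are never collected after Day 1 and are not collected in this study for rollover subjects. The visible text does not say what the total is when a part was not administered.

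**Working it through.** **The plan's own figure.** Maxima from the form in Protocol Appendix 2-10:

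- Part 1: 4 items × 4 = 16.
- Part 2: 13 items × 4 = 52.
- Part 3: items 18–19 (2 ratings), 20 (5), 21 (2), 22 (5), 23–26 (8) and 27–31 (5) make 27 component ratings; 27 × 4 = 108.
- Part 4: 13 + 7 + 3 = 23.
- Total: 16 + 52 + 108 + 23 = 199, as the SAP states.
- Parts 2 and 3: 52 + 108 = 160. Parts 1 and 4: 16 + 23 = 39, or 39/199 = 19.6% of the scale.

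**Unrated components.** Hold a component's true score at s (0 to 4) at both visits. The change produced by the rule is:

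- unrated after baseline only: −s
- unrated at baseline only: +s
- unrated at both visits: 0

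Let q0 and q1 be the probabilities of being unrated at baseline and after baseline. The mean spurious change is −s(q1 − q0). The documents give no unrated rates, so the values here are assumptions. With s = 1:

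- q0 = 0, q1 = 0.10: −0.10
- q0 = 0.05, q1 = 0.10: −0.05
- q0 = q1 = 0.10: 0
- q0 = 0.10, q1 = 0: +0.10

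The between-arm bias is the difference of this quantity between arms. It is 0 when the arms share the same s, q0 and q1.

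Ceiling for the hands-on items: rigidity 5 sites × 4 = 20, plus postural stability 4, gives 24 of 108 Part 3 points (22%), on 6 of 27 components.

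**Parts 1 and 4.** If the total is summed over whatever parts are available:

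- De Novo, Day 1 to any later visit: minus the Day 1 Part 1 + Part 4 score, so 0 to −39. If that score is 10%, 25% or 50% of 39 (assumed), the change is −3.9, −9.75 or −19.5.
- Rollover, Day 1 to any later visit: 0. Their Day 1 total has maximum 160, against 199 for De Novo subjects.
- Randomized comparison, V6 to V9: 0 in both arms, because both visits have Parts 2 and 3 only.

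**Effect of proration.** With 26 of 27 Part 3 components rated, all scored 1, the SAP rule gives 26. Proration gives 26 × 27/26 = 27.

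**The case against.** Much can be said for leaving the text alone.

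- *The randomized comparison is largely protected.* Loss of Parts 1 and 4 contributes exactly 0 from V6 to V9. One modality per subject is required across those visits, so an item that cannot be rated remotely would normally be unrated at both. Treatment is blinded, and nothing in the documents suggests unrated rates that differ by arm. This stands.
- *Remote rating may work.* Trained home-health staff are physically present at remote visits, and Protocol 6.4.10.5 lets the nurse assist the remote neurological examination, which includes tone and station. Detailed instructions are in a manual outside these documents. This stands as a reason not to assume that unrated items are frequent. It does not make the scoring rule right when one occurs.
- *The total may never be summed over two parts.* SAP 6.4.3 makes a change missing if either value is missing, so a total that cannot be formed could give no change at all. That reading is possible but not stated for the UPDRS total, and under it no total exists after Day 1.
- *Redaction.* SAP 8.7 is blacked out and may already name Parts 2 and 3 as the scores analysed. This stands; the point concerns only the visible scoring definition.

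A reader might infer that both rules always manufacture improvement. The documents do not support that: an item unrated only at baseline gives apparent worsening, and equal unrated rates cancel on average. Nor is 24 points a plausible effect. It is a scale ceiling, and SAP 8.7.1 reports Hoehn and Yahr stage 1, unilateral involvement, for almost all PD subjects entering randomized withdrawal.

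**Conclusion.** The scoring text should be corrected; severity is minor.

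The rule as written scores an unrated item as normal, in contrast to the averaging rule for the OHQ in the same section. Each component rated at only one of two visits adds a spurious change of up to 4 points, in a direction set by which visit lacks the rating. Bias between arms would require unrated rates that differ by arm. Otherwise the consequence is noise in one exploratory PD endpoint. This assumes constant true item scores; how often items go unrated is not known from the documents.

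The Parts 1–4 total is usable only as a De Novo Day 1 value. If it is summed over available parts, De Novo change from Day 1 is too low by 0 to 39 points, and Day 1 totals are not comparable between De Novo and rollover subjects, whom SAP 6.1 places side by side with a pooled column. This reaches descriptive open-label summaries only.

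**What to change.** In the UPDRS text of SAP 8.8:

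1. Prorate each part as the mean of its rated components times the number of components (27 for Part 3) when a pre-specified minimum is rated; otherwise set the part to missing. State the counting unit. It matters: with all six hands-on components unrated, 21/27 = 78% of components are rated but 12/14 = 86% of items, so an illustrative 80% minimum would reject the part on one count and accept it on the other. Component counting is preferable because Part 3 item maxima run from 4 to 20: prorating by item would give a maximally impaired subject 84/12 × 14 = 98 instead of 108. Add change on components rated at both visits as a sensitivity analysis.
2. Base every UPDRS change on Part 2, Part 3 and their sum. Report the Parts 1–4 total only as a De Novo Day 1 value.
3. Tabulate unrated items by arm, visit and visit modality.

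The cost is scoring text, derivation code and one table, with no new data as long as unrated items are recorded as such. The downside is that some part scores become missing.

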9. SAFETY AND TOLERABILITY

Analyses of safety and tolerability data include summaries of adverse events and summaries of drug exposure (duration of treatment), dosing information/compliance, concomitant medications, clinical laboratory test results, vital signs, ECGs, and C-SSRS responses.

All safety summaries will be presented separately for the open-label treatment period and the randomized withdrawal treatment period. Columns will be as specified in Section 6.1.

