8.6. Safety Analyses

Safety data, including C-SSRS, will be descriptively summarized separately for OL phase and double-blind randomized withdrawal phase.

The OL phase data will be summarized for all subjects and by enrollment group (De Novo Group or 0169 Completers Group), and the double-blind randomized withdrawal phase data will be summarized by treatment group according to treatment subjects received. Quantitative data collected at unscheduled times will be listed but will not be included in summaries. Categorical data collected at unscheduled times (e.g., ECG finding categories) will not be included in summaries by time point but will be included in summaries of findings during the entire treatment period.

Safety analyses will be performed using the safety analysis set. Unless specified otherwise, there will be no imputation of missing data in safety summaries. Subjects without post baseline measurement (e.g. ECG or vital signs) for a given time point will be excluded from the summary statistic (e.g., denominator of the summary statistic) for that time point.

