3. STUDY OBJECTIVES AND ENDPOINTS

3.1. Study Objectives

3.1.1. Primary Objective

The primary objectives are:

- To evaluate the durability of effect of TD-9855 in subjects with symptomatic neurogenic orthostatic hypotension (snOH) due to multiple system atrophy (MSA), Parkinson's disease (PD), or pure autonomic failure (PAF) compared with placebo over a double-blind, randomized withdrawal period of 6 weeks following an open-label phase of 16 weeks
- To evaluate the safety and tolerability of TD-9855 when taken for up to 22 weeks

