4. STUDY DESIGN

4.1. Overview

This is a Phase 3, multi-center, randomized withdrawal study to evaluate the sustained benefit in efficacy and safety of TD-9855 in subjects with primary autonomic failures (MSA, PD, or PAF) and snOH. The following is a summary of the study design. For a full description, refer to the study protocol.

Eligible subjects are either (i) completers of Study 0169 (0169 Completers Group), or (ii) snOH subjects meeting all applicable study inclusion criteria and none of the applicable exclusion criteria (De Novo Group). The principal eligibility criteria for the 0169 Completers Group are as follows:

- Subject has completed 4 weeks of double-blind treatment in Study 0169 (V6) and, in the opinion of the investigator, could benefit from continued treatment with amprelosetine. No minimum score of OHSAs#1 is required to enter V1 of Study 0170.
- Subject had $\geq 80\%$ study medication compliance in Study 0169

For the De Novo Group, the eligibility criteria are the same as for Study 0169. The principal criteria are as follows:

- Subject is male or female and ≥ 30 years old
- Subject meets the diagnostic criteria of symptomatic nOH, as demonstrated by a sustained reduction in BP of ≥ 20 mm Hg (systolic) or ≥ 10 mm Hg (diastolic) within 3 min of being tilted up $\geq 60^\circ$ from a supine position as determined by a tilt-table test
- Subject must score ≥ 4 on the OHSAs#1 at V1
- For subjects with PD only: Subject has a diagnosis of PD according to the United Kingdom Parkinson's Disease Society (UKPDS) Brain Bank Criteria (1992)
- For subjects with MSA only: Subject has a diagnosis of possible or probable MSA of the Parkinsonian subtype (MSA-P) or cerebellar subtype (MSA-C) according to The Gilman Criteria (2008)
- For subjects with PAF only: Subject has documented impaired autonomic reflexes, including the Valsalva maneuver performed within 24 months from the date of enrollment
- Subject has plasma norepinephrine levels ≥ 100 pg/mL after being in a seated position for 30 minutes

For the complete lists, refer to the Study 0169 and Study 0170 protocols.

The study has 3 periods: (i) 16-week open-label treatment with TD-9855, (ii) 6-week randomized treatment with blinded TD-9855 or blinded placebo, and (iii) 2-week follow-up (only for patients who do not enroll in Study 0171).

Subjects entering from Study 0169 (0169 Completers Group)

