6.1. Columns

Separate summaries will be provided for the open-label treatment period and the randomized withdrawal treatment period. For the open-label treatment period, summary tables will include the following columns:

- Placebo Study 0169 Completers (“0169 Placebo Rollover”)
- Amprexetine Study 0169 Completers (“0169 Amp Rollover”)
- De Novo Subjects (“De Novo”)
- All Subjects (“Total”)

For the randomized withdrawal treatment period, summary tables will include the following columns:

- Placebo (“Placebo”)
- Amprexetine (“TD-9855 10mg”)
- All Subjects (required only for study population and compliance summaries) (“Total”)

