6.3. Baseline Definition

For the open-label treatment period of the study, the baseline is the Study 0169 V6 (Week 4) assessment for subjects entering from Study 0169 and the V1 assessment for De Novo subjects. If a V1 assessment was not obtained for De Novo subjects, the latest earlier assessment will be used.

The assessments obtained at the Week 16 (V6, D113) visit in the open-label treatment period prior to randomization are considered the baseline assessments for the randomized withdrawal treatment period of the study.

Two variables have special baseline definitions, norepinephrine and smoking status. Details are given in the following sections.

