9.1. Adverse Events

Adverse events are collected from signing of the informed consent form through the end of follow-up. Adverse events will be coded to the preferred terms of the Medical Dictionary for Regulatory Activities (MedDRA®, version 24.1).

A treatment-emergent adverse event (TEAE) will be defined as any AE that begins on or after the date of first dose of study drug up through 14 days after the date of last dose of study drug. AEs that begin more than 14 days after the date of last dose of study drug and AEs that begin during the period from obtaining informed consent to the start of administration of study drug will not be considered treatment-emergent and will be listed only.

The following AE summaries will be provided for each treatment period:

- TEAE overall summary
- TEAEs by preferred term
- TEAEs by system organ class and preferred term
- Moderate or severe TEAEs by system organ class and preferred term
- TEAEs by preferred term with frequency > 3% of safety analysis set subjects
- TEAEs by system organ class, preferred term, and severity
- Drug-related TEAEs by system organ class and preferred term
- Drug-related TEAEs by system organ class, preferred term, and severity
- Drug-related moderate or severe TEAEs by system organ class and preferred term
- Serious TEAEs by system organ class and preferred term
- Drug-related serious TEAEs by system organ class and preferred term
- TEAEs resulting in on-study deaths
- TEAEs leading to premature study drug discontinuation
- TEAEs leading to temporary interruption of study drug
- TEAEs of special interest by system organ class and preferred term (Section 9.1.1)

If no adverse events meeting a specific table definition were reported, the body of the table will contain only a statement that no events met the table definition.

The following AE listings will be provided:

- TEAEs
- AEs leading to premature study drug discontinuation
- AEs resulting in temporary interruption of study drug
- Serious adverse events
- Deaths
- Non-treatment-emergent adverse events
- Adverse events of special interest (Section 9.1.1)
- Adverse events for excluded site 27045 (Section 6.2.1)

9.1.1. [REDACTED]

[REDACTED]

- [REDACTED]
- [REDACTED]
- [REDACTED]
- [REDACTED]
- [REDACTED]
- [REDACTED]

[REDACTED]

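### Safety over up to 22 weeks of TD-9855 is a primary objective, but no planned summary gives cumulative TD-9855 exposure and events, or change from a pre-drug baseline to Week 22

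*SAP*

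**What the plan says.** The second primary objective, in SAP 3.1.1 and Protocol 2.1, is: "To evaluate the safety and tolerability of TD-9855 when taken for up to 22 weeks". The 22 weeks are the sum of two treatment periods, as SAP 4.1 sets out: "The study has 3 periods: (i) 16-week open-label treatment with TD-9855, (ii) 6-week randomized treatment with blinded TD-9855 or blinded placebo".

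The reporting is split at the join between those periods:

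- SAP 9: "All safety summaries will be presented separately for the open-label treatment period and the randomized withdrawal treatment period". The same section lists drug exposure among these analyses.
- SAP 6.1: "Separate summaries will be provided for the open-label treatment period and the randomized withdrawal treatment period". The open-label columns are placebo rollovers from Study 0169, TD-9855 rollovers from Study 0169, De Novo subjects and a total. The randomized columns are placebo and TD-9855, with a total for some summaries.
- SAP 9.1: "The following AE summaries will be provided for each treatment period".
- Protocol 8.6: "Safety data, including C-SSRS, will be descriptively summarized separately for OL phase and double-blind randomized withdrawal phase".

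The baseline restarts as well. SAP 6.3 says of the randomized period: "The assessments obtained at the Week 16 (V6, D113) visit in the open-label treatment period prior to randomization are considered the baseline assessments". Table 3 in SAP 6.5 carries this through for vital signs, laboratory tests and ECGs, taking the last result before the first randomized dose. Protocol 8.1 likewise defines a baseline for each phase. The list of changes to protocol-specified analyses in SAP 11.2 adds no pooled safety output.

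**The concern.** The objective concerns continuous treatment across both periods, while each planned summary covers only one of them. Three quantities that a reader would want for this objective appear in no readable summary:

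- how many subjects took TD-9855 for how long in total, up to 22 weeks;
- the proportion with a treatment-emergent adverse event (TEAE), a serious adverse event (SAE) or an adverse event of special interest (AESI) while on TD-9855 over that time;
- the change in blood pressure, heart rate, ECG or laboratory values from before the drug to Week 22.

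The affected measures are ones the sponsor has singled out. Protocol 1.4 names increases in heart rate and blood pressure as important potential risks, and Protocol 7.1.4 makes supine hypertension an AESI. An effect that builds slowly over both periods, or that is established by Week 16 and then held, is the kind of effect that period-specific change tables show least well.

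**Working it through.** **Planned numbers.** Protocol 8.2 gives 154 randomized for 90% power at 25% against 50% failure, two-sided 0.05. The two-proportion formula without continuity correction gives 77 per arm, 154 in total, with power 0.901 at 77 per arm, so the figure reproduces. Enrolment is about 258: 258 × 0.60 = 154.8. With 1:1 allocation, 154 / 2 = 77 subjects stay on TD-9855 after Week 16. On the plan, then, about 258 are dosed, about 154 reach Week 16 on drug, and about 77 can reach Week 22 on drug.

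**Event incidence.** Let p1 be the incidence in the open-label period and p2 in the randomized period, for the same subjects. The 22-week incidence P satisfies

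max(p1, p2) ≤ P ≤ min(1, p1 + p2).

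The documents give no event rates, so these values are assumed:

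| p1 | p2 | Lowest P | Highest P | P if periods are independent |
|---|---|---|---|---|
| 20% | 10% | 20% | 30% | 28% |
| 40% | 20% | 40% | 60% | 52% |
| 50% | 30% | 50% | 80% | 65% |

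The last column is 1 − (1 − p1)(1 − p2). The planned tables do not supply p1 and p2 for the same subjects either. The open-label columns are organised by how subjects entered the study, not by the arm to which they were later randomized, so the open-label incidence for the roughly 77 continued subjects is not shown. Those subjects are also selected: Protocol 4.4 and 4.5 require a 2-point OHSA#1 improvement at Week 4, OHSA#1 no higher than 7, and at least 80% compliance.

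**Change from baseline.** Write B for the pre-drug value, W16 and W22 for the later ones. The open-label table reports W16 − B and the randomized table reports W22 − W16. The quantity wanted is W22 − B. If a shift is complete at Week 16 and held, W22 − W16 is about 0.

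**Change-based flags.** SAP 9.6 and its Table 10 band the QTcF change at 30 and 60 msec, and a listing picks out increases above 60 msec. Assume +40 msec at Week 16 and a further +30 msec by Week 22:

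- open-label period: +40, in the band above 30 and up to 60;
- randomized period: +30, in the band up to 30;
- total: 40 + 30 = +70, above 60, flagged in neither period.

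The listing would still include the subject if the absolute value reached 500 msec. Mean changes could be added roughly by eye. Individual flags cannot, because each is assessed against its own period's baseline.

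**Which pre-drug baseline.** Under SAP 6.3 the open-label baseline for Study 0169 completers is their Week 4 visit in that study. For those who received TD-9855 there, this is already an on-drug value. The protocol synopsis expects about 170 subjects from Study 0169. How many of them had taken TD-9855 is not given in these documents. For that group, even the open-label tables show no change from before the drug.

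**The case against.** The strongest reply is that by-period tables suit a randomized-withdrawal design, that protocol and SAP agree on them, and that two consecutive descriptive periods are a fair reading of safety for up to 22 weeks. All of that stands. There is no contradiction between the documents, and the by-period tables should stay.

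A reader might go further and infer that no table shows anything about safety at 22 weeks, or that the objective has no planned output. The documents do not support this. The randomized TD-9855 column reports TEAEs with onset in Weeks 17 to 22 in subjects on drug since the open-label period. Observed Week 22 laboratory, vital-sign and ECG values are summarised. The absolute limits in SAP Tables 9 and 10, such as systolic pressure above 160 mmHg or QTcF of 500 msec and over, do not depend on baseline. The reset affects change, shift and change-based outlier outputs, not event counts. Nor is every safety measure cut in two: ambulatory blood pressure is collected in the open-label period only.

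It can also be said that the two incidences can be multiplied together. That works only under independence between periods and with the same subjects in both, and neither is assured. By-subject listings would permit reconstruction, but they are not summaries.

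Two passages need care. Protocol 8.6 mentions findings over the whole treatment period, but only for unscheduled categorical data and after stating the split by phase. SAP 6.2.1 and 9.1.1 and part of section 6 are redacted, so a combined display there cannot be wholly excluded. The governing sentence in SAP 9 is readable and carries no exception.

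**Conclusion.** The point holds as a gap between a primary objective and its reporting. In the readable text, no summary gives total TD-9855 exposure, cumulative TEAE, SAE or AESI incidence on TD-9855 over 22 weeks, or change from a pre-drug baseline to Week 22. The consequences are that a sustained shift reads as about zero in the randomized period, and that a QTcF increase above 60 msec spread over both periods can escape the change-based tables and listing.

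The size depends on data not in the documents. The incidence ranges and the 40 + 30 msec example are assumptions that show what the layout can hide; they do not predict what will be found. The figures of 258, 154 and 77 are planned numbers, and the SAP allows for early termination by the sponsor, so fewer subjects may reach Week 22. The efficacy conclusion is unaffected. This is an inexpensive improvement that answers a stated objective more directly.

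**What to change.** Keep the by-period tables and add to SAP 9 an overall TD-9855 exposure summary:

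- **Set and time at risk.** All subjects dosed with TD-9855 in Study 0170, from first to last TD-9855 dose in this study. Censor subjects randomized to placebo at their first placebo dose. State any carry-over window, since Protocol 1.3.1 gives a half-life of about 30 to 40 hours.
- **Content.** Duration of exposure; TEAE, SAE and AESI tables; and, in the arm kept on TD-9855, vital-sign, ECG and laboratory changes and outlier flags through Week 22.
- **Baseline.** A pre-TD-9855 value: the Study 0169 baseline for subjects who took TD-9855 in that study, and the open-label baseline for De Novo subjects and placebo rollovers. SAP 6.3.1 already uses the Study 0169 baseline for norepinephrine in rollovers, so there is a precedent.
- **Labelling.** For TD-9855 rollovers the change then spans up to 4 + 22 = 26 weeks of treatment. Say so in a footnote or show them separately.

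The cost is SAP wording, a few extra tables and use of Study 0169 baseline data. No new data collection is needed, and the sample size does not change.
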